7.3 Lost to Follow-up

A participant will be considered lost to follow-up if her or his parents or LARs cannot be contacted by the site or designee.

The following actions must be taken if the parents or LARs of the participants do not follow-up on the monthly electronic contact (until 6 months after dosing/randomization) or cannot be contacted by phone at the end of the study as planned in the SoA:

- For the monthly electronic contact: the electronic platform will send one reminder for 3 consecutive days. If there is no answer after the e-reminders, the site and/or designee will call the parents or LARs of the participant as soon as possible, discuss the importance of answering the follow-up questions with them, and ascertain whether or not they wish their infant to continue participating in the study.
 - It is to be noted that if both the electronic and phone reminders fail, the next monthly electronic contact (up until 6 months post-dosing/randomization) will take place. The participant will not be deemed lost to follow-up before the 12-months follow-up phone contact for France, Germany, and UK non-reconsented participants or the 24-months follow-up phone contact for UK reconsented participants takes place.
- For the 12 months follow-up phone contact for France, Germany, and UK non-reconsented participants or the 24 months follow-up phone contact for UK reconsented participants, and before a participant is deemed lost to follow-up, the investigator or designee must make every effort to regain contact with the parents or LARs of the participants (where possible, 3 telephone calls and, if necessary, a certified letter to the participant's last known mailing address or local equivalent methods). These contact attempts should be documented in the participant's medical record.
 - Should the parents or LARs continue to be unreachable, the participant will be considered lost to follow-up.

Discontinuation of specific sites or of the study as a whole are handled as part of Appendix 10.1.

8 Study Assessments and Procedures

- Study procedures and their timing are summarized in the SoA. Protocol waivers or exemptions are not allowed.
- Adherence to the study design requirements, including those specified in the SoA, is essential and required for study conduct.
- All screening evaluations must be completed and reviewed to confirm that potential participants meet all eligibility criteria. The investigator will maintain a screening log to record details of all participants screened and to confirm eligibility or record reasons for screening failure, as applicable.

8.1 Efficacy Assessments

Planned time points for all efficacy assessments are provided in the SoA.

Efficacy data for the first year of study and descriptive data for the second year of the study are collected through the participant's medical records and reported in the eCRF. Hospitalizations will be reported by parents/LARs of participants through an eDiary for the first year of the study. From D01 to D366, each time a health event will be captured on the eDiary, a medical call center will contact parents/LARs to collect and report the health event's information in the eCRF. The Investigator or delegated site staff will review information reported in the eCRF and interview the participants' parents/LARs if any additional information needs to be collected. Parents/LARs who don't have access to the eDiary will be requested to contact directly the investigation site to report any health event.

From D366 to D731, UK reconsented participants' parents/LARs will record in the memory aid any hospitalization that occurred. During the 18-month and 24 month phone calls, the Investigator or delegated site staff will interview parents/LARs to collect information reported in the memory aid and report only LRTI hospitalization's information in the eCRF.

During the 12- and 24-month follow-up calls, the site investigator or staff designee will ask to parents/LARs of UK reconsented participants if the participants had experienced any medically attended cough, chest or breathing problems throughout the study period. After the 12-month follow-up phone call (when possible) and the 24-month follow-up phone call, the site investigator or staff designee (including third parties authorized by the site investigators) will access the UK reconsented participants' medical record (general practitioner's or hospital's record) to determine if the medical event meets with the definition of wheeze provided by the Sponsor (see Section 8.1.2.4). If so, the event and related complementary information (including any medications prescribed during wheeze) will be retrospectively collected.

8.1.1 Baseline Assessments at the Time of Immunization

All parents or LARs will be asked to provide demographic information on the participant such as gestational age, date of birth (or month of birth, depending on local regulations), weight, gender, medical history, vaccine history, and postal code at the time of enrollment. The type of demographic information collected is determined by laws in each country.

8.1.2 Efficacy Assessments

Efficacy assessments will be based on RSV LRTI hospitalization throughout the study period (Section 8.1.2.2), and very severe RSV LRTI (Section 8.1.2.3) throughout the first year of the study (see Section 8.1.2.1), through 150 days post-dosing/randomization, and through 180 days post-dosing/randomization as described in Section 3.

8.1.2.1 Definitions

"Hospitalization" is defined as the decision to admit to in-patient care by the treating physician.

"RSV season" is the period of increased RSV infection. For the purpose of efficacy analyses, the start and end dates of the RSV season will be defined on a country-by-country basis and will be based on country-specific epidemiological surveillance.

8.1.2.2 RSV LRTI Hospitalization

Participants will be monitored for RSV LRTI hospitalization.

Parents or LARs can report the hospitalization through the eDiary (for the first year of the study for all the participants) which will trigger a contact by the site and/or designee. Site staff and/or designee will inquire about the hospitalization and report it in the eCRF. For the second year of the study, parents or LARs of UK reconsented participants will report hospitalizations in a memory aid. Information reported in the memory aid will be collected by sites during the 18-month and 24-month phone calls.

Whether a hospitalization is effectively due to an RSV LRTI or not will be assessed by the Investigator:

- If the attending physician is the Investigator, the assessment of the case will be done directly as the participant information (eg, RSV test result and medical interventions) will be readily available.
- If the attending physician is not the Investigator, the collection of participant information will be done retrospectively. In this situation, the Investigator or designee will seek the required information from the facility where medical attention was sought to complete the participant's electronic case report form (eCRF).

Based on the information captured, the Investigator will assess whether hospitalization was due to RSV LRTI and categorize the case accordingly. It is to be noted that testing for RSV is expected to be performed by the hospital as part of routine practice.

Symptoms commonly associated with LRTI include (but are not limited to):

- Clinical finding of rhonchi, rales, crackles, or wheeze,
- Increased respiratory rate at rest (age: < 2 months, ≥ 60 breaths/min; 2 to 6 months, ≥ 50 breaths/min; > 6 months, ≥ 40 breaths/min),
- Hypoxemia (in room air: oxygen saturation < 95%)

Each potential case of RSV LRTI hospitalization should be documented with the RSV test result, the lowest rate of oxygen saturation recorded, duration of hospital stay, and the list of medical interventions leading to end of the hospitalization (eg, oxygen supplementation, intravenous fluid administration, admission to intensive care unit).

It is to be noted that, for hospitalization due to respiratory infection, parents or LAR of the participant will be instructed to present the participant card (paper version or digital version through the eDiary) to the hospital. RSV test will be performed at the hospital as part of routine practice. The participant card will contain a reminder for RSV testing.

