1.1 Synopsis

Protocol Title:

A Phase IIIb randomized open-label study of nirsevimab (versus no intervention) in preventing hospitalizations due to respiratory syncytial virus in infants (HARMONIE)

Brief Title:

Study of a single intramuscular dose of nirsevimab in the prevention of hospitalizations due to respiratory syncytial virus (RSV) infection in healthy term and preterm infants during the first year of life

Rationale:

This study is being proposed to collect and analyze data on the safety of the monoclonal antibody (nirsevimab) and its efficacy compared to that of no intervention in preventing hospitalizations^a for lower respiratory tract infection (LRTI) due to RSV as confirmed by test (henceforth referred to as RSV LRTI hospitalization). Data will be collected from infants born during the RSV season as well as from infants born out of RSV season. The typical RSV season in the Northern Hemisphere spans approximately 5 months and usually starts in October or November. As the start and end dates of the RSV season may change in response to the actual circulation of RSV, in this study, the RSV season will be defined on country-by-country basis and will be based on country-specific epidemiological surveillance.

The study will also assess health care utilization parameters associated with hospitalization for LRTI due to RSV as confirmed by test. This could provide some insights into the potential benefits of an all-infant nirsevimab implementation strategy.

^a "Hospitalization" is defined as the decision to admit to in-patient care by the treating physician.

Objectives and Endpoints:

Objectives	Endpoints				
Primary					
To assess the efficacy of nirsevimab in preventing RSV LRTI hospitalization compared to no intervention	Overall incidence of RSV LRTI hospitalization through the RSV season				
Key Secondary					
To assess the efficacy of nirsevimab in preventing very severe RSV LRTI compared to no intervention	Incidence of very severe RSV LRTI defined as RSV LRTI hospitalization with oxygen saturation < 90% (at any time during hospitalization) and oxygen supplementation, through the RSV season				
To assess the efficacy of nirsevimab in preventing RSV LRTI hospitalization compared to no intervention in each country	Incidence of RSV LRTI hospitalization through the RSV season in each country				

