Infant RSV LRTI hospitalization has been selected as the primary endpoint since hospitalization for LRTI due to RSV is a significant part of RSV burden of disease and the assessment of cases does not impose additional clinical procedures on participants or parents/LARs. The assessment of very severe RSV LRTI cases will be used as one of the main secondary endpoints as it will allow evaluating the impact of nirsevimab on the incidence of RSV infection in its rarer but direst manifestations.

This study's design does not permit blinding. Parents/LARs will know whether their infant received the study intervention or not and, depending on the enrollment setting (eg, hospital or medical office), the child's pediatrician or the family doctor may be the person performing inclusion in the study, administering or not administering the study intervention, and later advising parents/LARs on the course of action in case of respiratory infection. These "real-world" conditions are bound to introduce some bias that the use of a blind assessor or of an adjudicating committee would not entirely alleviate (55). However, and although this study is open-labelled, the selection of a very robust and patient-oriented endpoint kernel (ie, RSV LRTI hospitalization) will allow for a scientifically sound and clinically relevant assessment of nirsevimab efficacy.

Despite being a monoclonal antibody, nirsevimab will be administered by intramuscular injection like routine pediatric vaccinations. Furthermore, nirsevimab can be co-administered along with routine pediatric vaccines planned in the vaccination schedule of each country (53). This will facilitate its administration during routine appointments, making it possible to immunize the entire intervention cohort at the start of the season using existing healthcare appointments when possible. This, in line with the mostly pragmatic study design, will further help minimize the burden on parents/LARs of participants and on the healthcare system of each country.

Rationale for the Study Population

The participants to be enrolled are all infants from France, Germany, and UK, under the age of 12 months entering their first RSV season that are not eligible to receive RSV prophylaxis with palivizumab, which indication is limited to infants with certain underlying conditions such as chronic lung disease, congenital heart disease, or very premature.

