6.3.2 Blinding and Code-breaking Procedures

Code-breaking procedures are not applicable as this is an open-label study.

Blinding remains a methodological safeguard in clinical trials and is important for limiting bias, such as selection bias, detection bias, and performance bias. In this open-label pragmatic study, nirsevimab immunization will be compared to standard-of-care, ie, no intervention, and having a blinded third party or clinician assessing the patient outcomes is not feasible. Whether the compared groups will receive similar amount of attention cannot be ensured and this, in turn, can result in biased treatment effect estimates with uncertainties on the direction of the bias (underascertainment/over-ascertainment). Methods that decrease risk of bias will be used, such as standardization of questionnaires, a narrowly-defined and objective primary outcome, and when possible electronic health records to retrieve the primary clinical endpoints. Response rates to the questionnaires between the 2 groups will inform about the risk of bias.

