Hospitalizations due respiratory illness (including cases of very severe RSV LRTI) will be reported in a specific eCRF page.

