9.4.2 Primary Endpoint

The primary endpoint is the overall incidence of RSV LRTI hospitalization through the RSV season in healthy term and preterm infants in all 3 countries combined. The determination of RSV LRTI hospitalization is based on the criteria described in Section 8.1.2.2.

The efficacy of nirsevimab in preventing RSV LRTI hospitalization compared to no intervention will be estimated accounting for the follow-up time post-dosing/randomization up to the data cut-off date for the Primary Analysis as follows:

 $(1-(CN/NN)/(CC/NC)) \times 100\%$

where:

- CN and CC are the numbers of RSV LRTI hospitalization through the RSV season in the nirsevimab and the control (ie, no intervention) groups, respectively.
- NN and NC are the total person-time contributed by participants randomized in the nirsevimab and the control groups, respectively.

The 95% CI for the efficacy will be calculated by an exact method assuming a binomial distribution of the number of RSV LRTI hospitalizations in the nirsevimab group conditional on the total number in both groups accounting for the follow-up time post-dosing/randomization.

The superior efficacy of nirsevimab in preventing RSV LRTI hospitalization will be concluded if the lower bound of the efficacy is > 0%. The primary efficacy analysis of the primary endpoint will be performed on all randomized participants.

If a participant experiences multiple occurrences of the same primary endpoint, only the first episode will be considered. The following rules will be applied in the calculation of the total person-time for the follow-up time:

- The start date for the follow-up will be the date of randomization for participants who are randomized to no intervention and the date of dosing for participants who are randomized to nirsevimab.
- For the participants who do not have the primary endpoint at the time of the Primary Analysis, the end date for the efficacy follow-up will be the end of the RSV season, or the last available date with confirmation of no RSV LRTI hospitalization for the Primary Analysis whichever is earlier. The efficacy follow-up will be censored at the end date.
- For the participants who have the primary endpoint at the time of the Primary Analysis, the end date for the efficacy follow-up will be the date of hospital admission.

The above-described analysis on the primary endpoint will also be conducted on the PPAS.

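### The primary event rests on the unblinded investigator's RSV attribution, with no written positive-test condition, although the plan calls the outcome test-confirmed and objective

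*Protocol*

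**What the plan says.** Protocol 9.4.2 sends the reader elsewhere for the primary event: "The determination of RSV LRTI hospitalization is based on the criteria described in Section 8.1.2.2". In Protocol 8.1.2.2 the operative sentences are "Whether a hospitalization is effectively due to an RSV LRTI or not will be assessed by the Investigator" and "Based on the information captured, the Investigator will assess whether hospitalization was due to RSV LRTI and categorize the case accordingly". The section lists signs of LRTI as an open list. It asks that each potential case be documented with its RSV test result, but does not say that the result must be positive. Testing follows hospital routine, prompted by a reminder on the participant card.

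SAP 2.4 defines hospitalization and RSV season only. SAP 6.6.1 counts RSV LRTI hospitalizations without deriving them from eCRF fields. Very severe RSV LRTI (Protocol 8.1.2.3) and the per-country endpoint (Protocol 9.4.3.2) are built on the same event.

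Elsewhere the outcome is described differently. The synopsis rationale speaks of hospitalization for LRTI "due to RSV as confirmed by test (henceforth referred to as RSV LRTI hospitalization"). Protocol 6.3.2 says that blinded outcome assessment is not feasible, and names among its measures against bias "standardization of questionnaires, a narrowly-defined and objective primary outcome". Protocol 4.2 acknowledges that the child's own doctor "may be the person performing inclusion in the study, administering or not administering the study intervention".

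**The concern.** The plan gives up blinding and relies on the objectivity of the endpoint instead. The property that would make RSV status objective, a positive test, is not written into the section that decides what counts. As written, an investigator who knows the allocation may class a test-positive LRTI admission as not due to RSV, and that infant becomes a non-event. If this happens more often in the nirsevimab arm, the numerator of the primary endpoint is biased, and with it those of the very severe and per-country endpoints, which is the whole confirmatory hierarchy. This step can be removed without a blinded reader, because Protocol 8.7 already requires the RSV test result for every LRTI hospitalization.

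**Working it through.** **1. The plan's own figures.** Inputs from Protocol 9.2: control incidence 1.1%, efficacy 60% (rate ratio 0.40), 9620 participants per country (4810 per arm), two-sided alpha 1.66%.

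- Expected events per country: 4810 × (0.011 + 0.0044) = 74.07, matching the stated 74.
- Exact conditional binomial test, nirsevimab share 0.5 under the null and 0.4/1.4 = 0.286 under the alternative: 74 events give 91.4% power at alpha 1.66%; 61 events give 92.2% at alpha 5%.

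The event counts reproduce. The point concerns what is counted, not how many events are needed.

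**2. The passages side by side.**

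| Place | What settles RSV status |
|---|---|
| Protocol 1.1, rationale | A test |
| Protocol 6.3.2 | An outcome described as objective |
| Protocol 8.1.2.2, used by 9.4.2 | The investigator's categorisation; test result documented, positivity not required |
| SAP 2.4 and 6.6.1 | Not stated |
| SAP 6.6.2.2 (tipping point) | Test missing or not done is treated as missing outcome |

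The last row suggests that the analysts expect test status to matter, but no counting rule says so. A test-positive admission attributed elsewhere is not missing, so the tipping-point analysis leaves it as a non-event.

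**3. Size of the bias.** The documents give no misattribution rate, so the share *m* of nirsevimab-arm cases attributed elsewhere is an assumption, with none in the control arm and equal person-time. Observed efficacy = 1 − 0.4 × (1 − *m*):

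- *m* = 5%: 1 − 0.4 × 0.95 = 62%
- *m* = 10%: 1 − 0.4 × 0.90 = 64%
- *m* = 20%: 1 − 0.4 × 0.80 = 68%

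**4. Could it change the conclusion?** Exact conditional (Clopper-Pearson) limits, equal person-time:

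| Nirsevimab vs control events | Efficacy (95% CI) | p |
|---|---|---|
| 17 vs 44 (61 events, near the planned effect) | 61.4% (31.0 to 79.3) | 0.0007 |
| 25 vs 36 (61 events, weak effect) | 30.6% (−18.9 to 60.0) | 0.20 |
| 21 vs 36 (four relabelled) | 41.7% (−2.7 to 67.6) | 0.063 |
| 20 vs 36 (five relabelled) | 44.4% (1.4 to 69.5) | 0.044 |

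Near the planned effect, superiority is clear without any relabelling. Only a much weaker effect, with five of 25 cases (20%) moved in one direction, crosses the line.

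**5. With no true effect.** If nirsevimab cases are counted a fraction *d* less often, their share of events is (1 − *d*)/(2 − *d*). At 61 events superiority needs 22 or fewer in the nirsevimab arm. The chance of a false claim is 2.0% at *d* = 0, 5.0% at 10% and 11.7% at 20%. At about 174 events (14 430 × 0.0086 × 1.4 = 173.7) it is 2.0%, 8.8% and 28.0%. These too are assumed rates.

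**The case against.** The strongest reply has four parts.

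- **The bias is disclosed.** Protocol 4.2 and 6.3.2 acknowledge it and call its direction uncertain. That stands, and the calculations above take only the direction that favours nirsevimab. Disclosure is still no reason to keep a judgement step that existing data could remove.
- **Other analyses already look at this.** All-cause LRTI hospitalization through the season (SAP 6.6.4.3.1) is unaffected by moving a case from RSV to non-RSV LRTI. The post-hoc all-cause hospitalization analysis (SAP 6.6.9.1) needs no attribution at all. SAP 6.6.7.4 tabulates RSV test status by arm. These are real checks, but less specific or incomplete: none compares the test result with the investigator's category.
- **The documents intend a positive test.** A reader might infer from 8.1.2.2 that an untested control infant could be counted as a case. The documents do not support that reading: the synopsis requires confirmation by test, and SAP 6.6.2.2 treats an untested admission as missing. Section 8.1.2.2 is silent on positivity rather than opposed to it. What remains is that the operative section lacks the rule.
- **A test rule is not judgement-free.** A reader might infer that the collected result would define the event without judgement. It would not; it settles RSV status only. Admission is the treating physician's decision (Protocol 8.1.2.1), testing follows hospital routine, and LRTI rests on an open list of signs. A test-positive infant admitted under a label such as poor feeding, not classed as LRTI, would still be missed.

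**Conclusion.** The point holds in limited form. RSV attribution for the primary event is left to an unblinded investigator with no stated positive-test condition. The plan's case for objectivity needs that condition, and the tipping-point analysis does not examine test-positive admissions attributed elsewhere. It should be corrected.

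The size is unknown. Under the assumed one-way misattribution of 5% to 20%, a true efficacy of 60% would read as 62% to 68%. A reader might infer from the 25 vs 36 example that relabelling could manufacture the trial's success. The documents do not support that: they give no misattribution rate, the example lies far from the planned effect and at the edge of significance, and its 56 counted events fall below the 61-event trigger. At the planned effect the harm is an inflated estimate.

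**What to change.** 1. In Protocol 8.1.2.2 and SAP 2.4 and 6.6.1, count an event as an LRTI hospitalization recorded in the eCRF with a documented positive RSV test, whatever the investigator's RSV attribution. Keep the investigator's categorisation as a sensitivity analysis, and say how untested and discordant admissions are handled.
2. If the Primary Analysis has already been run, do not replace the primary event. Report the test-based version as a labelled supplementary analysis. This looks like the applicable case: Protocol 9.4.1 sets 30 April 2023 as the latest date, and section 7 of the SAP, whose document history runs to January 2025, refers to that analysis in the past tense. If the programs already required a positive test, stating so is enough for this step.
3. Add a supplementary analysis of any admission on the respiratory page with a positive RSV test. Protocol 8.2.3 says that admissions for respiratory illness "will be reported in a specific eCRF page"; I assume that this page holds the test result. This drops the LRTI label but still depends on the admission being entered as respiratory.
4. Tabulate by arm the RSV testing rate among LRTI admissions and the cross-classification of test result against investigator category. SAP 6.6.7.4 already supplies the test counts.

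The cost is SAP wording and a few tables from data already collected, with no extra reader or test. The downside is that a few incidental test-positive admissions may be counted in both arms, slightly lowering specificity. The change removes the RSV-attribution step only. The decision to admit, the decision to test and the LRTI label stay unblinded.
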